#### 6.7.3.2. Lesion Counts

The mean change from baseline to Week 16 for the total number of abscesses, inflammatory nodules, draining fistulae, and abscess and inflammatory nodule (AN) will be individually summarized and assessed using ANCOVA. Moreover, we will calculate the proportion of patients that achieve 50%, 75% and 90% decreases in AN count at W12 and W16. In addition to AN reduction, the proportion of patients with disease flare will be calculated up to W16, defined as a  $\geq 25\%$  increase in AN count from the baseline and  $\geq 2$  in AN count.

### 6.7.3.3. Modified Sartorius Score (mSS)

The mean percent change from baseline to Week 16 for the total modified Sartorius Score (mSS) will be summarized by treatment group and assessed using MMRM methods.

### 6.7.3.4. International Hidradenitis Suppurativa Severity Score System (IHS4)

The mean percent change from baseline to Week 16 for the International Hidradenitis Suppurativa Severity Score System (IHS4) will be summarized by treatment group and assessed using MMRM methods.

### 6.7.3.5. Patient-Reported Outcomes

Categorical variables will be analyzed using logistic regression analyses, whereas the mixed-effects model of repeated measures (MMRM) will be the method of analysis for continuous endpoints. The analyses will be based on the mITT population unless otherwise specified.

The following continuous endpoints from patient-reported outcomes will be assessed:

- Mean change from baseline to Week 16 on the Dermatology Life Quality Index (DLQI)
- Mean change from baseline to Week 16 on the Drainage Numeric Rating Scale
- Mean change from baseline to Week 16 on the Smell Numeric Rating Scale

The following categorical endpoints from patient-reported outcomes will be assessed:

- Proportion of patients responding “no symptoms” on the Patient Global Impression of Severity – 7 Days (Hidradenitis Suppurativa)
- Proportion of patients responding “much better” on the Patient Global Impression of Change – 7 Days (Hidradenitis Suppurativa)
- Proportion of patients responding “much better” or “a little better” on the Patient Global Impression of Change – 7 Days (Hidradenitis Suppurativa)
- Proportion of patients with baseline skin pain NRS $\geq$ 3 having a decrease in skin pain NRS $\geq$  30%
- Proportion of patients with baseline drainage NRS $\geq$ 3 having a decrease in drainage NRS $\geq$  30%
- Proportion of patients with baseline smell NRS $\geq$ 3 having a decrease in smell NRS $\geq$  30%

For patients who meet the criteria at baseline for the presence of inflammatory back pain (IBP), the following endpoints will be assessed using ANCOVA:

- Mean change from baseline to Week 16 on the weekly spinal pain numeric rating scale
- Mean change from baseline to Week 16 on the weekly nightly spinal pain numeric rating scale.

### 6.7.3.6. Pharmacokinetic Analyses

Plasma concentrations of LY3041658 will be listed by time point using descriptive statistics and displayed graphically. Actual sampling time relative to the last dose and time deviations will be considered to determine exclusions from summary statistics and mean plots.

The data may also be analyzed using a population approach via nonlinear mixed-effects modeling (NONMEM) with the NONMEM software. The PK data from Study DSAD may be combined with data from another study in the clinical development program to improve PK parameter estimation.

#### **6.7.3.7. Immunogenicity**

Frequencies and percentages will be tabulated for the following:

- participants with pre-existing ADA, and
- participants who are TE-ADA positive (TE-ADA+) to LY3041658.

Treatment-emergent ADAs are defined as those with a titer 2-fold (1 dilution) greater than the minimum required dilution if no ADAs were detected at baseline (treatment-induced ADA) or those with a 4-fold (2 dilutions) increase in titer compared with baseline if ADAs were detected at baseline (treatment-boosted ADA). For the TE-ADA+ participants, the distribution of maximum titers will be described. The frequency of neutralizing antibodies, if assessed, may also be tabulated for the TE-ADA+ participants.

The relationship between the presence of ADA and the LY3041658 concentrations and PD response to LY3041658, including safety and efficacy, may also be assessed.

### **6.8. Bioanalytical and Pharmacokinetic/Pharmacodynamic Methods**

Graphical analyses to explore relationships between LY3041658 exposure and select biomarkers and clinical efficacy endpoints will be performed.

### **6.9. Safety Analyses**

The general methods used to summarize safety data, including the definitions of baseline values, are described in Section 6.3.2.

Safety analyses will include data after rescue unless otherwise stated, and patients will be analyzed according to the investigational product to which they were randomized at Week 0 (Visit 2). Additional analyses may be conducted using data after rescue to systemic therapy for some safety topics such as systemic treatment-emergent adverse events (TEAEs), and serious adverse events (SAEs). Safety analyses will take place using the safety population defined in Section 6.3.1.

Safety topics that will be addressed include the following: AEs, clinical laboratory evaluations, vital signs and physical characteristics.

Unless otherwise specified, by-visit summaries will include planned on-treatment visits. For tables that summarize events (such as AEs, categorical lab abnormalities, shift to maximum value), post-last dose follow-up data will be provided for Treatment Period 1 (Week 0 to Week 16) and Treatment Period 2 (Week 16 to Week 36) separately. For deaths and malignancies, all

available follow-up data up to the end of the study will be included. Listings will include all safety data.

For selected safety assessments, descriptive statistics may be presented for the last measure observed during post-treatment follow-up (up to 30 days after the last dose of treatment including rescue, regardless of the study period).

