9.4.5. Safety Analyses

Safety analyses will include adverse events, SAEs, AESIs, C-SSRS, vital signs, ECGs, and laboratory analytes, using the Safety Population data descriptively summarized by treatment group. Categorical safety measures will be summarized with incidence rates. Continuous safety measures will be summarized as mean change by visit. Exposure to study intervention will be calculated for each participant and summarized by treatment group.

Adverse events will be coded according to the *Medical Dictionary for Regulatory Activities* (MedDRA) and summarized by system organ class (SOC), preferred term, severity, and

relationship to the study intervention. A treatment-emergent adverse event (TEAE) is defined as an event that first occurred or worsened in severity after baseline, with baseline defined as all pre-existing conditions recorded at Visit 1 and any adverse events recorded before the first dose of study intervention (that is, during the interval between Visits 1 and 2 and recorded with the time of onset before the first dose of study intervention). The treatment periods will be used as the postbaseline period for the analysis. Safety analyses will be conducted separately for each treatment period. For events that are gender specific, the denominator and computation of the percentage will include only participants from the given gender.

The number and percentage of participants who experienced TEAEs, TEAEs by maximum severity, deaths, SAEs, TEAEs related to study intervention, discontinuations from the treatment due to an adverse event, and AESIs will be summarized. Treatment-emergent adverse events (all, by maximum severity), SAEs including deaths, and adverse events that lead to treatment discontinuation will be summarized and analyzed by MedDRA SOC and preferred term.

Treatment-related TEAEs (TEAEs related to study intervention) are defined as events that are indicated by the investigator on the eCRF to be related to treatment.

Adverse events of special interest will be identified by a standardized MedDRA query (SMQ) or a Lilly-defined MedDRA preferred term listing.

Suicide-related thoughts and behaviors occurring during treatment will be summarized based on responses to the C-SSRS consistent with the C-SSRS Scoring and Data Analysis Guide (Columbia Lighthouse Project WWW).

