### 6.3. General Considerations

Efficacy analyses will be conducted on the Modified Intent-to-Treat (mITT) and Per-Protocol Set Population. The mITT set includes all data from all randomized participants receiving at least 1 dose of the IP according to the treatment the participants were assigned. The PPS set includes all data from all randomized participants who missed no more than 1 dose of study treatment to which they were assigned up to and including Week 14.

Safety analyses will be conducted on the Safety Population. This set includes all data from all randomized participants receiving at least 1 dose of the IP according to the treatment the participants actually received.

All tests of treatment effects will be conducted at a 2-sided alpha level of 0.05, unless otherwise stated. All confidence intervals (CIs) will be given at a 2-sided 95% level. Descriptive summaries of continuous data will present the group mean, standard deviation, median, minimum, maximum, and sample size. Descriptive summaries of discrete data will report the number of participants and incidence as a frequency and as a percentage. All p-values will be rounded up to 3 decimal places.

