#### 6.3.1. Analysis Populations

The following populations are defined for this study:

Population	Description
Entered	All participants who sign the informed consent form
Modified Intent-to-Treat (mITT)	All participants randomly assigned to study intervention and who receive at least 1 dose of study intervention. Participants will be analyzed according to the intervention to which they were assigned.
Per Protocol Set (PPS)	All participants randomly assigned to study intervention to which they were assigned at Week 0 and who missed no more than 1 dose of study treatment up to and including Week 14.
Safety	All participants randomly assigned to study intervention and who receive at least 1 dose of study intervention. Participants will be analyzed according to the intervention they actually received within each study period.
Pharmacokinetic (PK) Analysis	All participants randomly assigned to study intervention and who receive at least 1 dose of study intervention and have PK data available.

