### **6.9.2. Adverse Events**

Adverse events are recorded in the eCRFs. Each AE will be coded to system organ class (SOC) and preferred term (PT) using the Medical Dictionary for Regulatory Activities (MedDRA) version that is current at the time of database lock. Severity of AEs is recorded as mild, moderate, or severe.

A TEAE is defined as an event that either first occurred or worsened in severity after the first dose of study treatment and on or prior to the last visit date during the analysis period. For each event classification term, the number of participants experiencing a TEAE with that classification term will be tabulated. TEAEs will be summarized by treatment period and overall for the study.

Treatment-related TEAEs are defined as events that are indicated by the investigator on the eCRF to be related to treatment. For events that are gender-specific, the denominator and computation of the percentage will include only participants from the given gender.

Adverse events are classified based upon the MedDRA PT. The MedDRA Lowest Level Term (LLT) will be used in defining which events are treatment-emergent. The maximum severity for each LLT during the baseline period up to the first dose of the study medication will be used as the baseline. If an event with missing severity is preexisting during the baseline period, and persists during the treatment period, then the baseline severity will be considered mild for determining TEAE (that is, the event is treatment-emergent if the severity is coded moderate or severe postbaseline and not treatment-emergent if the severity is coded mild postbaseline). If an event occurring postbaseline has a missing severity rating, then the event is considered treatment-emergent. The day and time for events where onset is on the day of the first dose of study treatment will both be used to distinguish between pretreatment and posttreatment in order to derive treatment-emergence. Should there be insufficient data for AE start date to make this

comparison (for example, the AE start year is the same as the treatment start year, but the AE start month and day are missing), the AE will be considered treatment-emergent.

In an overview table, the number and percentage of subjects who experienced a TEAE or serious adverse event (SAE), died due to an AE, or discontinued from the study due to an AE will be summarized by treatment.

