The frequency and percentages of patients with TEAEs will be summarized by treatment using MedDRA PT nested within SOC. Events will be ordered by decreasing frequency within SOC. The frequency and percentages of patients with TEAEs by maximum severity will also be summarized by treatment using MedDRA PT nested within SOC.

Fisher's exact test will be performed to compare percentages for each LY3041658 dose group and Placebo at both the SOC and PT levels.

Listings will be presented for all AEs, all SAEs, all AEs leading to death, all AEs leading to study drug temporary interruption, and all AEs leading to discontinuation from the study.

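### SAP 6.9 groups safety data by the product randomised at Week 0, contradicting the Safety Population it invokes in the same paragraph; in summaries that cross Week 16, the Week 0 rule books LY3041658 events under placebo

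*SAP*

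**What the plan says.** Two grouping rules stand in one paragraph of SAP 6.9 (Safety Analyses).

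- The first is by original assignment: "patients will be analyzed according to the investigational product to which they were randomized at Week 0 (Visit 2".
- The second is by reference: "Safety analyses will take place using the safety population defined in Section 6.3.1". In SAP 6.3.1 that population carries its own rule: "Participants will be analyzed according to the intervention they actually received within each study period". Protocol 9.3 defines it in the same way. SAP 6.3 and protocol 9.4.1 also group safety data "according to the treatment the participants actually received".

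No text says which rule prevails, and no placebo-to-LY3041658 column is defined.

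The places where the choice matters are these:

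- **Switch.** From Week 16 all participants receive LY3041658 (protocol 4.1, SAP 5.1).
- **TEAEs.** SAP 6.9.2: "TEAEs will be summarized by treatment period and overall for the study". Protocol 9.4.5 names only by-period analyses: "Safety analyses will be conducted separately for each treatment period".
- **Deaths and malignancies.** SAP 6.9 says that all "available follow-up data up to the end of the study will be included".
- **Test.** SAP 6.9.2 says that Fisher's exact test "will be performed to compare percentages for each LY3041658 dose group and Placebo at both the SOC and PT levels", with no period named.

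**The concern.** A programmer who follows the Week 0 sentence keeps every placebo participant in the placebo column for the whole study. Any summary that runs past Week 16 then counts events that arose on LY3041658 as placebo events. The two columns become more alike, so a true excess on drug looks smaller. A death or malignancy on drug in a former placebo participant could be displayed as a placebo case. With about 21 placebo participants, one such case would read 1/21 (4.8%) against 0/42. Safety is a stated purpose of this study, and the placebo arm is too small to absorb misattributed events.

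**Working it through.** **Inputs.** Periods of 5 (screening), 16, 20 and 10 weeks; dosing every 2 weeks, last dose at Week 34; planned arms of 42 and 21 (protocol 9.2) or 34 and 17 (SAP 6.2). The documents give no adverse event rates, so the rates in step 4 are assumptions.

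**1. The plan's own timeline.** 5 + 16 + 20 + 10 = 51 weeks, which reproduces the stated duration.

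**2. One placebo completer under the Week 0 rule.**

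- Infusions: Weeks 0 to 14 give 8 of placebo; Weeks 16 to 34 give 10 of LY3041658. 10/18 = 55.6%.
- Treatment weeks: 20/36 = 55.6% are on LY3041658.
- Time to the last visit: (46 − 16)/46 = 30/46 = 65.2% falls after the switch. Weeks 36 to 46 of this are off-dose follow-up.

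**3. The whole placebo column, Weeks 0 to 36.**

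- If all 21 complete: 21 × 20 / (21 × 36) = 420/756 = 55.6%. The SAP's 17 give 340/612, the same share.
- With dropout: protocol 9.2 expects about 45 of 63 to complete Period 1. Applied equally to both arms (assumed), that is 21 × 45/63 = 15. If the other 6 stop at Week 2, 8 or 14 (assumed), the share is 300/552 = 54.3%, 300/588 = 51.0% or 300/624 = 48.1%.
- Grouped as received within each period, no LY3041658 time falls under placebo.

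**4. Illustration of the dilution (assumed rates, constant hazard, full follow-up).** Let p0 be the 16-week placebo risk, λ = −ln(1 − p0)/16, and HR the hazard ratio. With p0 = 10% and HR = 3:

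| Table | LY3041658 | Placebo column | Ratio |
|---|---|---|---|
| Period 1 | 1 − exp(−16·3λ) = 27.1% | 10.0% | 2.71 |
| Whole study, Week 0 rule | 1 − exp(−36·3λ) = 50.9% | 1 − exp(−16λ − 20·3λ) = 39.4% | 1.29 |
| Whole study, placebo throughout (hypothetical) | 50.9% | 1 − exp(−36λ) = 21.1% | 2.41 |

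The third row shows that longer follow-up explains only the fall from 2.71 to 2.41. The fall from 2.41 to 1.29 comes from mixing. Exact two-sided Fisher power at 42 v 21 is 31% in Period 1 and 11% in the whole-study table.

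Over p0 = 5%, 10%, 20% and HR = 2, 3, 5, the Period 1 ratio is 1.80 to 4.52 and the whole-study ratio is 1.15 to 1.41. With the step 3 dropout in both arms, the p0 = 10%, HR = 3 whole-study ratio is 1.31 to 1.41.

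**5. Check on a tempting repair: raw percentages by treatment at onset.** Take no drug effect and p0 = 10%. On LY3041658, 42 participants have 36 weeks (21.1%) and 21 have 20 weeks (1 − exp(−20λ) = 12.3%). Pooled: (42 × 21.1% + 21 × 12.3%)/63 = 18.2%. On placebo, 21 have 16 weeks: 10%. The ratio is 1.82 (1.72 to 1.87 over p0 of 20% to 5%), produced by unequal exposure alone.

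**The case against.** The strongest reply is that the Week 0 phrase works as a sequence label. SAP 6.7.3.1 shows Week 0 to 36 efficacy by original arm, and a safety table labelled in that way would be readable. This has force for Period 2 and whole-study displays. But the SAP defines no such label for safety, and the phrase still conflicts with the population named in the same paragraph.

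Other limits stand:

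- **Fisher test on the whole-study table.** A reader might infer that this is planned. SAP 6.9.2 is only silent on the period, while protocol 9.4.5 points to separate periods. The diluted test is a conditional consequence.
- **Malignancies by arm.** A reader might infer a planned table that shows on-drug malignancies as placebo cases. SAP 6.9 says which follow-up is included but specifies no by-arm malignancy table. The 1/21 v 0/42 example applies only if such a display is made.
- **SAE and AE-discontinuation tables.** SAP 6.9.2.1 and 6.9.2.2 refer to a study drug period that is not defined. They cross Week 16 only if that term covers both periods.
- **The rule alone is not enough.** Grouping as received within each period does not place a switched participant in a single whole-study column, so that table needs its own instruction.

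**Conclusion.** The concern holds in this limited form. The contradiction is textual and certain, and should be fixed. Its effect is confined to summaries that cross Week 16: the whole-study TEAE summary, and any by-treatment display of deaths or malignancies that uses all follow-up.

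For a placebo completer, 20 of 36 treatment weeks would be booked to the wrong treatment. Across the column the share is about 48% to 56%, depending on the assumed dropout. The ratios and powers illustrate direction only, because they rest on assumed rates, a constant hazard and, except where dropout is stated, full follow-up.

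A reader might infer that the placebo-controlled safety comparison is lost. The documents do not support that. The Period 1 TEAE table is still produced, and there the two rules differ only for dosing errors. Listings include all safety data, and the primary endpoint is untouched.

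**What to change.** 1. In SAP 6.9, replace the Week 0 rule with grouping by the intervention received in each period. Label Period 2 columns placebo-to-LY3041658 and LY3041658-to-LY3041658.
2. Limit placebo comparisons and Fisher tests to Period 1, ending before the Visit 10 dose. Define the study drug period in SAP 6.9.2.1 and 6.9.2.2 with the same limit.
3. Show whole-study TEAEs, deaths and malignancies by sequence, labelled as not a placebo comparison. Treatment at onset is an alternative only with exposure-adjusted rates (events per person-time), for the reason in step 5 of the working.

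Minor and separate: state in SAP 6.3.2 and protocol 9.4.1 that the Visit 10 pre-dose value counts towards the Period 2 baseline, and assign events dated on Visit 10 by onset relative to that day's dose. The documents do not show that onset time is collected on that date, so a default is needed where it is missing.

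The cost is SAP wording, one baseline sentence in the protocol and table programming. Study conduct does not change, unless the sponsor chooses to collect onset time at Visit 10.
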